### 4.1. Randomization and Stratification

Not applicable.

### 4.2. Schedule of Administration

For subjects continuing on duvelisib treatment, subjects will self-administer duvelisib orally BID (28 days = 1 cycle) as a capsule formulation. Subjects will continue on the same dose level they last received in their previous duvelisib study.

#### 4.2.1. Dose Modifications

Up to 2 dose reductions are allowed, based on the subject's starting dose in this study:

| Starting Dose | Dose Level -1 | Dose Level -2 |
|---------------|---------------|---------------|
| 75 mg BID     | 50 mg BID     | 25 mg BID     |
| 50 mg BID     | 25 mg BID     | 15 mg BID     |
| 25 mg BID     | 15 mg BID     | 10 mg BID     |

|           |           |    |
|-----------|-----------|----|
| 15 mg BID | 10 mg BID | NA |
|-----------|-----------|----|

Abbreviations: BID = twice a day; NA = not applicable.

Note: No dosing below 10 mg BID is allowed.

Dose holds up to 42 days are permitted for management of treatment-related AEs. For subjects only being followed for OS, no duvelisib will be administered.

### 4.3. Treatment Discontinuation

Treatment discontinuation occurs when a subject is no longer receiving any duvelisib. A subject should be discontinued from duvelisib if, in the opinion of the Investigator, it is medically necessary, or if it is the wish of the subject.

Subjects will be discontinued from treatment in case of any of the following reasons:

- An AE or unacceptable toxicity that requires discontinuation of duvelisib
- Disease progression
- Subject death
- Noncompliance to protocol
- Investigator decision
- Subject becomes pregnant
- Subject lost to follow-up
- Termination of the study by the Sponsor
- Voluntary withdrawal from study treatment by subject

Adverse events leading to the discontinuation of a subject will be followed until the event resolves, resolves to baseline, or is considered stable or chronic.

If a subject discontinues duvelisib, then a Treatment Termination (TT) Visit should occur within 7 days after the last dose of duvelisib. Each TT assessment need not be performed if the subject has had all the same assessments within the previous 2 weeks.

All subjects receiving duvelisib will have a Safety Follow-up visit approximately 30 (+ 7) days after the last dose of duvelisib. If possible, this visit should occur before the initiation of any subsequent anticancer therapy. At a minimum, this visit should include collection of AEs/serious AEs (SAEs), and concomitant medications/procedures. This follow-up visit may be performed by telephone call as long as the subject does not require laboratory and/or other procedures related to any new or ongoing AEs, in which case a clinic visit will be required.

Subjects who discontinue duvelisib and have not withdrawn consent from overall study participation will enter the survival follow-up period described in [Section 6.5](#).

#### 4.4. Study Discontinuation/Withdrawal

Subjects may discontinue/withdraw from the study for any of the following reasons without prejudice:

- Subject death
- Subject lost to follow-up
- Completion of the follow-up period
- Termination of the study by the Sponsor
- Voluntary withdrawal from study by subject

If the subject withdraws consent from overall study participation (and not just treatment with duvelisib), then no further attempts should be made to collect additional data from the subject.

## 5. STUDY POPULATION

The study population will consist of subjects who received treatment with duvelisib or participated in the survival follow-up phase in a previous duvelisib study.

The number of subjects will be based on the number of eligible subjects on previous duvelisib studies approved for this long-term continued treatment and follow-up study.

### 5.1. Inclusion Criteria

To be eligible to participate in the study, all subjects must:

1. Have participated in a previous study of duvelisib, and:
  - a. Be actively receiving duvelisib monotherapy on the previous study (within 14 days of study entry) and demonstrating clinical benefit (CR/PR/SD) of continued use, *or*
  - b. Be in the survival follow-up phase of a previous duvelisib study
2. Have completed the required components of the previous study and be appropriate for enrollment into this long-term continued treatment and follow-up study, as determined by the Sponsor
3. Understand and voluntarily sign the informed consent form (ICF) before the conduct of any study-related procedures/assessments

To be eligible to participate in the study, subjects actively receiving duvelisib must:

1. Have a negative serum or urine  $\beta$  human chorionic gonadotropin ( $\beta$ -hCG) pregnancy test if a woman of child-bearing potential (WCBP). WCBP are defined as sexually mature women who have not undergone surgical sterilization or who are not naturally postmenopausal for at least 24 consecutive months (women  $\leq$  55 years) or 12 consecutive months (women  $>$  55 years)
2. Agree to use adequate methods of birth control throughout the study and for 30 days after the last dose of duvelisib for all WCBP, all sexually active male subjects, and all partners of subjects

### 5.2. Exclusion Criteria

Any subject is to be excluded from the study if he or she:

1. Is unwilling or unable to comply with the requirements of the protocol

Subjects actively receiving duvelisib are to be excluded from this study if they:

1. Have any ongoing  $\geq$  Grade 3 AE considered related to duvelisib treatment at screening
2. Are pregnant or nursing

## 6. STUDY PROCEDURES AND ASSESSMENTS

Time points for assessments to be collected throughout the study can be found in [Table 1](#) for subjects continuing duvelisib treatment and [Table 2](#) for subjects being followed for OS. A brief description of each of these assessments can be found below.

### 6.1. Screening Assessments for All Subjects

Before starting screening assessments, the Investigator (or Investigator's designee) will discuss with the potential study subject the nature of the study and its risks, requirements, and restrictions, and will obtain written informed consent. During the screening period, a unique subject identification number will be assigned.

Screening assessments are described in [Table 1](#) for subjects continuing duvelisib treatment and [Table 2](#) for subjects being followed for OS. Procedures captured on the previous duvelisib study within 30 days of Cycle 1 Day 1 (C1D1) do not need to be repeated. However, for WCBP receiving duvelisib, the C1D1 pregnancy test must be performed within 7 days before the first dose to confirm eligibility.

#### 6.1.1. Informed Consent

Subjects potentially eligible for participation must sign an ICF before initiating any study-specific procedures or assessments. Standard-of-care assessments that fulfill study eligibility requirements may be performed before the subject signs the ICF.

#### 6.1.2. Inclusion and Exclusion Criteria

Inclusion and exclusion criteria ([Section 5.1](#) and [Section 5.2](#), respectively) will be reviewed for each potential subject and documented in the subject medical record and electronic case report form (eCRF).

### 6.2. Treatment Assessments for Subjects Receiving Duvelisib

Subjects receiving duvelisib treatment will have the following assessments performed according to [Table 1](#). Subjects enrolled in the survival follow-up portion of the study will be assessed as described in [Section 6.5](#).

#### 6.2.1. Concomitant Medication and Therapies

Assessment of concomitant medications and procedures will be performed according to [Table 1](#).

#### 6.2.2. Initial (Cycle 1 Day 1) Physical Examination and Disease-related Symptom Assessment

The initial physical examination (PE) will be performed at C1D1 and will include vital sign measurements (temperature, blood pressure [after the subject has been seated for at least 5 minutes], pulse rate, and respiratory rate), height, and weight, and liver and spleen assessments. The initial PE will also include review of disease-related symptoms (symptoms of fever [ie, temperature  $> 38^{\circ}\text{C}/100.4^{\circ}\text{F}$ ] without evidence of infection, weight loss, and drenching night sweats without evidence of infection).

### 6.2.3. Focused Physical Examination and Disease-related Symptom Assessment

Subsequent PEs will be focused and include liver and spleen assessments and review of disease-related symptoms (symptoms of fever [ie, temperature  $> 38^{\circ}\text{C}/100.4^{\circ}\text{F}$ ] without evidence of infection, weight loss, and drenching night sweats without evidence of infection). Any new clinically significant abnormality from baseline should be recorded as an AE.

### 6.2.4. Clinical Laboratory Tests

Clinical laboratory tests include hematology with 5-part differential, chemistry panel, liver function tests (LFTs), and serum or urine  $\beta$ -hCG pregnancy tests. These laboratory tests will be performed throughout the study to monitor safety as presented in [Table 1](#). In addition, monitoring of subjects receiving anticoagulation therapy should be done as clinically appropriate.

Laboratory assessments captured on the previous duvelisib study within 30 days of C1D1 do not need to be repeated at the C1D1 visit.

The following laboratory parameters will be measured and analyzed locally:

- Hematology laboratory parameters include red blood cell (RBC) count, hemoglobin, hematocrit, and white blood cell count with differential to include an absolute neutrophil count.
- Chemistry laboratory parameters include albumin, total protein, uric acid, sodium, potassium, calcium, phosphorous, chloride, bicarbonate (or  $\text{CO}_2$ ), blood urea nitrogen or urea, creatinine, lipase, amylase, magnesium, and glucose.
- Liver function tests include lactate dehydrogenase, serum alanine aminotransferase (ALT), serum aspartate aminotransferase (AST), total and direct bilirubin, and alkaline phosphatase.
- A serum or urine  $\beta$ -hCG pregnancy test should be performed within 7 days before the first dose to confirm eligibility. If negative test results are available from the subject's previous duvelisib study within this time, the test does not need to be repeated. While subjects are receiving duvelisib, serum or urine pregnancy tests will be repeated every 3 cycles.

Unscheduled assessments should be done as clinically indicated.

Clinically significant abnormal laboratory test results, including but not limited to those findings resulting in a drug hold/reduction/discontinuation or medical intervention, should be reported as an AE (see [Section 8.1.1](#) for definition of an AE). In the presence of Grade 3 or higher cytopenias, more frequent monitoring per institutional guidelines is recommended.

### 6.2.5. Radiographic Assessment

Radiologic evaluations performed on the previous duvelisib study within 60 days of C1D1 do not need to be repeated at the C1D1 visit. Radiologic evaluations will be performed once a year, approximately 1 year from the most recent scan on the previous duvelisib study. Magnetic

resonance imaging may be substituted if clinically indicated, but the modality chosen to evaluate each individual subject should be the same as the previous duvelisib study and maintained throughout the duration of this study.

#### 6.2.6. Investigator Response Assessment

Disease response assessments should be performed as needed or no later than every 12 months while the subject is receiving treatment.

All response assessments are to be completed as applicable to disease type. The modality chosen to evaluate each individual subject should be the same as in the previous duvelisib study and maintained throughout the duration of the study. The subject's entire duvelisib treatment course, including the previous duvelisib study, should be considered when determining response or progression. Baseline for evaluating response is the baseline of the previous study.

Given the diversity of the disease types being enrolled, it is beyond the scope of this protocol to list all of the response criteria that will be used to evaluate efficacy. [Table 3](#) shows the major criteria employed for disease response assessment.

**Table 3: Disease Response Criteria**

| Disease type           | Examples of tumor assessment include:                          | Efficacy criteria                                 |
|------------------------|--|---|
| Lymphoma (except CTCL) | CT scan of chest, abdomen, and pelvis; FDG-PET where indicated | IWG criteria (Cheson et al, 2007)     |
| CTCL                   | Skin assessments   | mSWAT (Olsen et al, 2011)             |
| CLL                    | CT scan of chest, abdomen, and pelvis; complete blood count    | NCI-WG criteria (Hallek et al, 2008)  |

Abbreviations: CLL = chronic lymphocytic leukemia; CT = computed tomography; CTCL = cutaneous T-cell lymphoma; FDG = [F]fluorodeoxyglucose; IWG = International Working Group; mSWAT = modified Skin

Weighted Assessment Tool; NCI-WG = National Cancer Institute-sponsored Working Group; PET = positron emission tomography.

Note: Tumor assessments shown are examples and not necessarily comprehensive of the requirements needed for associated disease-specific efficacy criteria.

In this long-term extension study, a blinded central review of response assessments will not be performed. In addition, the following items are not required for investigator response assessments:

- Bone marrow biopsies and bone marrow aspirates, and
- Blood samples to determine minimal residual disease.

Adverse events, including SAEs, associated with any disease assessment must be collected as described in [Section 8.2](#).

#### 6.2.7. Adverse Events

Any ongoing AEs from the previous duvelisib study must be  $\leq$  Grade 3 at the time of entry into this study. Any new or worsening preexisting medical conditions arising after the subject signs the ICF but before the first dose of duvelisib on this study will be captured as the subject's medical history. For all subjects continuing duvelisib treatment, AEs should be monitored from the time the subject takes the first dose of duvelisib on this study (C1D1) through 30 days after the last dose of duvelisib.

All SAEs for all subjects will be reported from the time the subject signs the ICF until 30 days after the last dose of duvelisib. If an Investigator becomes aware of an SAE that he or she considers to be related to duvelisib at any time after completion of the AE reporting period (ie, 30 days after the last dose of duvelisib), the event must be reported.

See [Section 8.2](#) for a full description of the collection and reporting of AEs during this study.

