## 8. SAFETY DATA COLLECTION, RECORDING AND REPORTING

### 8.1. Adverse Events

#### 8.1.1. Definition of an Adverse Event

An AE is defined as any untoward medical occurrence in a patient or clinical investigation subject administered a pharmaceutical product and that does not necessarily have to have a causal relationship to this treatment.

An AE can, therefore, be any unfavorable and unintended sign (including an abnormal laboratory finding, for example), symptom, or disease temporally associated with the use of the medicinal product, whether or not considered related to the medicinal product.

Adverse events include worsening of a preexisting medical condition as well as clinically significant changes from baseline laboratory values or conditions. Worsening of the preexisting medical condition (eg, diabetes, hypertension) means that it has increased in severity, frequency, and/or duration, and/or has an association with a significantly worse outcome. A preexisting condition that has not worsened during the study is not considered an AE.

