## 8.2. Procedures for Eliciting, Recording, and Reporting Adverse Events

### 8.2.1. Eliciting and Recording Adverse Events

Subjects will be instructed to report all AEs and will be asked a general health status question at each study visit. All AEs occurring in eligible subjects will be recorded in the eCRF from the time the subject takes the first dose of duvelisib on this study (C1D1) through 30 days after the last dose of duvelisib. An AE will be followed until it is either resolved, has returned to baseline, or is determined to be a stable or chronic condition. All SAEs occurring from the signing of the ICF through 30 days after the last dose of duvelisib will be processed as outlined in [Section 8.2.2.](#)

At each required visit during the trial, all AEs that have occurred since the previous visit must be reviewed by the Investigator or designee. The Investigator or designee must determine if the AE is serious or nonserious.

The Investigator must assign the following AE attributes:

- AE diagnosis or syndrome(s) if known
  - If not known at time of the report, record the signs and/or symptoms as AEs and provide an updated report with diagnosis when obtained
- Dates of onset and resolution
- Severity as defined in this protocol
- Assessment of relatedness to duvelisib, and
- Action taken with duvelisib as a result of the AE

In general, an AE that is the primary cause of subsequent events should be identified by the primary cause (eg, for dehydration due to diarrhea, the AE would be diarrhea). However, AEs occurring secondary to an initiating event that are separated in time should be recorded as independent events (eg, sepsis secondary to pneumonia, both events should be recorded).

Progression of disease should not be reported as an AE/SAE but rather the signs and/or symptoms manifesting as the progression of disease should be reported (eg, for dyspnea due to progression of disease, the AE would be dyspnea). All fatal events must be reported as an SAE.

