### 9.4. Safety Analyses

Adverse events will be coded by using the Medical Dictionary for Regulatory Activities (MedDRA) version 16.1 or higher and will be graded according to the CTCAE, version 4.03 or higher.

Summaries of AEs will be focused on treatment-emergent AEs (TEAEs). In this long-term extension study, a TEAE is defined as any AE with an onset date on or after C1D1 and within 30 days after the last dose of duvelisib. TEAEs will be summarized by MedDRA system organ class and preferred term. Separate summaries for TEAEs related to duvelisib, TEAEs that led to treatment discontinuation, TEAEs that led to death, TEAEs by CTCAE grade, TEAEs of Grade 3 or higher, serious TEAEs, and serious TEAEs related to duvelisib will be provided.

Baseline laboratory values will be those collected at C1D1 of this long-term extension study, or if not available, the most recent values collected within 30 days before C1D1. Applicable laboratory values will be graded according to CTCAE criteria. Shifts from baseline to maximum postbaseline grades will be tabulated for hematology, blood chemistry, and LFTs.

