7.1.2 Demographic and Disease History

Demographic will be summarized. The variables will include age, age group (<65 versus >=65), sex, race, ethnicity, height and weight. Disease history will be summarized. Diagnoses include (Chronic Lymphocytic Leukemia (CLL), chronic lymphocytic leukemia/small lymphocytic lymphoma (CLL/SLL), follicular lymphoma (FL), diffuse large B-cell lymphoma (DLBCL), Waldenstrom macroglobulinemia (WM)).

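### Non-serious, non-laboratory toxicity carried over from the parent study has no planned output in this extension unless it worsens, and the protocol and SAP definitions of a treatment-emergent AE differ on such events

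*Protocol*

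**What the plan says.** Subjects who continue treatment must have been on duvelisib monotherapy in the parent study within 14 days of entry (Protocol 5.1). They carry on at the same dose level (4.2).

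Four rules decide what becomes an AE in this study:

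- Protocol 6.2.7, repeated in Table 1 footnote l, covers the gap between consent and first dose. A condition that first appears or gets worse once consent is given, yet "before the first dose of duvelisib on this study will be captured as the subject's medical history".
- Protocol 8.2.1 starts recording with the extension's own first dose: "All AEs occurring in eligible subjects will be recorded in the eCRF from the time the subject takes the first dose of duvelisib". Serious AEs (SAEs) are the exception and are reported from consent.
- Protocol 8.1.1 counts worsening of an existing condition as an AE, but adds: "A preexisting condition that has not worsened during the study is not considered an AE".
- Protocol 9.4 sets the window for the tables: "a TEAE is defined as any AE with an onset date on or after C1D1", up to 30 days past the last dose.

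SAP 7.3.1 words the TEAE differently. It compares onset only with the last dose date plus 30 days and states no lower bound. SAP 8.1, which lists changes from the protocol, does not mention this.

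The protocol expects ongoing parent-study AEs at entry, because 6.2.7 sets a grade limit for them. For outputs, SAP 7.1.2 says "Disease history will be summarized" alongside demographics, and 7.3.1 covers TEAEs and AEs of special interest. SAP 6.9 names a dictionary for coding medical history, but no section tabulates it.

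**The concern.** The primary objective is long-term safety, and AEs are a primary endpoint. For a subject already on drug, C1D1 marks a change of protocol and not a change of exposure. Toxicity that began in the parent study and persists, such as low-grade diarrhoea or rash, is part of what a long-term extension should describe.

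The protocol takes the other approach for response. Section 6.2.6 uses the parent-study baseline and considers the whole duvelisib course. Safety restarts at C1D1, and no reason is given for the difference.

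Two things are at stake. The tables may understate the toxicity that subjects live with on long-term treatment. And two planned tables can disagree on how many subjects stopped treatment for toxicity. In addition, the duty in 8.2.1 to assign severity, relatedness and action taken attaches to AEs, so an event filed as medical history carries no such requirement.

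**Working it through.** No arithmetic applies: the plan gives no sample size, event count or power figure, and SAP 3.5 plans no inferential analysis. The check is to trace each kind of carried-over event through the rules.

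| Event | Recorded as | TEAE under Protocol 9.4 | TEAE under SAP 7.3.1 |
|---|---|---|---|
| 1. Non-serious parent-study AE, ongoing and unchanged | Not an AE (8.1.1) | No | Only if a site enters it on the AE form |
| 2. Same AE, worsens after C1D1 | AE (8.1.1) | Yes, if onset is dated at worsening; no rule says so | Yes |
| 3. Non-serious event, new or worse between consent and C1D1 | Medical history (6.2.7) | No | No, because it is not on the AE form |
| 4. SAE between consent and C1D1 | Reported as an SAE (6.2.7, 8.2.2) | No | Yes, if held in the AE data |
| 5. Laboratory abnormality carried over | Baseline grade in the shift table (9.4) | No, unless it becomes a reportable AE | Only if on the AE form |

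**Outputs.** Cases 1 and 3 reach no planned table. SAP 7.1.2 covers demographics and disease history, SAP 7.3.1 covers TEAEs and AEs of special interest, and neither document plans pooling with parent-study AEs. Case 2 reaches the TEAE tables. Case 4 is reported, but falls outside TEAE tables built on the protocol definition. Case 5 is visible as a baseline grade.

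**Discontinuation.** Take a subject who stops because of a case 1 event.

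- Protocol 4.3 lists an AE or unacceptable toxicity as a reason for stopping, and SAP 7.1.1 tabulates the primary reason. The subject counts as 1 in disposition.
- Onset precedes C1D1, so under Protocol 9.4 the subject counts as 0 among TEAEs leading to discontinuation.
- The two tables differ by one for each such subject.

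**Does the SAP wording close the gap?** Only for events already on the AE form, and recording there starts at C1D1. If a site does enter a carried-over event, the SAP rule counts it as treatment-emergent and mixes old onset with new. A completely missing start date is also counted as treatment-emergent (SAP 6.2.1).

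**The case against.** The strongest reply is that a TEAE table reports new or worsened events by design. The study is descriptive, and Protocol 9.4 states the C1D1 start openly. That stands as a defence of the TEAE definition. It does not explain why persisting toxicity has no other output.

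A reader might infer that carried-over toxicity never appears in the primary safety results. The documents do not support that:

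- Worsening in severity, frequency or duration is an AE (8.1.1). Because duration is included, some sites might record persistent diarrhoea and others not.
- SAEs are reported from consent.
- Laboratory abnormalities show as the baseline grade, and those that lead to a change in study drug should be reported as AEs (6.2.4, 8.2.1.3).
- Section 5.2 excludes subjects with ongoing related AEs of Grade 3 or higher, which bounds what can be carried over under that section.

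A reader might also infer that the data are lost. The parent protocols are not available here and may well record these events. What is shown is that this study's tables omit them. The medical history sentence covers only consent to first dose, and Table 1 places consent in the C1D1 column, so that window may be short. For events that began earlier, the operative rules are 8.1.1, 8.2.1 and 9.4.

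Nor can a multiple be put on the understatement. For example, 10 new and 20 ongoing cases among 100 subjects would give 10% in the table against 30% affected, but all three inputs are assumed and the comparison sets incidence against prevalence.

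The discontinuation mismatch needs a subject to stop for an event that has not worsened. That may be uncommon, but cumulative intolerance of a stable event is possible and the plan does not provide for it.

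**Conclusion.** The point holds in a limited form and should be fixed. Under the stated rules, non-serious, non-laboratory toxicity that is ongoing at C1D1, or that arises between consent and C1D1, has no planned output in this study unless it worsens. A discontinuation caused by it can appear in disposition but not among protocol-defined TEAEs leading to discontinuation. The size is unknown, since the documents give no count of subjects entering with ongoing AEs.

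The conclusion assumes that sites follow 8.1.1 and 8.2.1 as written and that the Protocol 9.4 definition governs. If the SAP wording governs instead, carried-over events that sites happen to enter would be counted as treatment-emergent, which is a different fault. Either way, the two definitions must be reconciled.

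**What to change.** 1. In Protocol 6.2.7, 8.2.1 and Table 1 footnote l, record on the AE eCRF both AEs ongoing at C1D1 and AEs arising between consent and C1D1. Capture original onset date, grade at C1D1, relatedness, outcome and an ongoing-at-entry flag. Say in 8.1.1 how this fits with the rule on unworsened conditions.
2. In SAP 7.3.1, adopt the Protocol 9.4 window: onset no earlier than C1D1 and no later than 30 days past the last dose. Date a worsening at the time it occurs. This must go with step 1. Under the present SAP wording, entering events with their original onset dates would put all of them into the TEAE tables. If the SAP keeps a different definition, list it in SAP 8.1.
3. Add one table of flagged AEs by preferred term and grade, showing their course: resolved, unchanged, worsened, or led to dose change or discontinuation. Show flagged events on a separate line in the summary of AEs leading to discontinuation, so that it agrees with disposition.

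The cost is one eCRF flag, some extra data entry at rollover, one table, and wording changes in both documents.

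Separately, the entry grade limits must be reconciled. Section 6.2.7 and Table 1 footnote l allow ongoing AEs up to and including Grade 3, while 5.2 excludes ongoing related AEs of Grade 3 or higher. A related Grade 3 AE meets one rule and fails the other.
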